9.4.3.2. Action Taken for Adverse Events

For each reported adverse event, an Investigator must document the action taken according to the following criteria:

- No action
- Concomitant medication
- Hospitalization or prolongation of hospitalization
- Study discontinued
- Nondrug therapy
- Other (specify)

The Investigator must also document the action taken with study drug (as a result of a given adverse event) according to the following criteria:

- Dose not changed
- Study drug interrupted
- Study drug withdrawn
- Not applicable
- Unknown

9.4.3.3. Outcome for Adverse Events

Adverse events should be followed until resolution. For each reported adverse event, the Investigator must document the outcome according to the following criteria:

- Fatal
- Not recovered/not resolved
- Recovered/resolved
- Recovered/resolved with sequelae
- Recovering/resolving
- Unknown

9.5. Serious Adverse Events

Serious adverse event reporting will begin at the time informed consent is obtained and will end 30 days after the last dose of study drug. SAEs must be reported to the sponsor or designee using the provided form either by email or fax to the following email address or fax number, respectively:

- [REDACTED]

- [REDACTED]

A serious adverse event is any adverse event occurring at any dose that results in any of the following outcomes:

- Death: “Death” is an outcome and is NOT the adverse event. In the event of death, the cause of death should be recorded as the adverse event. The only exception is “sudden death” when the cause is unknown.
- Is a life-threatening experience: Life-threatening adverse events include any adverse drug experience that, in the view of the Investigator, places the subject at immediate risk of death from the reaction as it occurs. It does not include a reaction that, had it occurred in a more serious form, might have caused death.
- Requires inpatient hospitalization or prolongation of existing hospitalization
- Results in a persistent or significant disability/incapacity: Disability is defined as a substantial disruption in a person’s ability to conduct normal life functions.
- Results in a congenital anomaly/birth defect.
- Additionally, important medical events that may not result in death, be life-threatening, or require hospitalization may be considered a serious adverse event when, based upon appropriate medical judgment, they may jeopardize the subject and may require medical or surgical intervention to prevent one of the outcomes listed previously (eg, allergic bronchospasm requiring intensive treatment in an emergency room or at home).

All serious adverse events that result in death or are life threatening, regardless of causal relationship, must be reported to the Sponsor-designated Medical Monitor within 24 hours of the site’s knowledge of the event. A copy of the initial serious adverse event report must be received within one (1) business day.

All other serious adverse events or other events reportable to the United States Food and Drug Administration (FDA) and/or IRB will be forwarded to the Sponsor-designated Medical Monitor within one (1) business day.

Any reported cases of COVID-19 that meet the SAE criteria above should be reported as per the protocol’s defined SAE process.

The serious adverse event report should provide as much of the required information as is available at the time. The following minimum information is required for reporting a serious adverse event: subject identification, reporting source, and an event outcome. Supplemental information may be transmitted using a follow-up report and should not delay the initial report. Aptinyx or its representative may contact the investigational site to solicit additional information or to follow-up on the event.

If there is any doubt whether the information constitutes a serious adverse event, the information will be treated as a serious adverse event for the purposes of this protocol. Serious adverse event reporting will begin at the time of consent and will end 30 days after the last dose.

All relevant documentation pertaining to a serious adverse event (eg, additional laboratory tests, consultation reports, discharge summaries, and postmortem reports) will be provided to the Sponsor -designated Medical Monitor in a timely manner. Serious adverse events will be

followed until resolution or return to baseline (when worsening of a pre-existing condition is reported). If a serious adverse event does not return to baseline but reaches a stable situation that is not expected to change, this may be documented on the serious adverse event form.

The Sponsor may break the treatment code for subjects who experience a serious adverse event in order to determine if the individual case or group of cases requires expedited regulatory reporting. Individual treatment codes will be available to limited staff who are responsible to break codes for reporting purposes.

For each SAE, the Investigator and Sponsor will independently assess whether there is a reasonable possibility that the event may have been caused by the study drug (“drug-related”). The Sponsor will evaluate each drug-related SAE to determine if the event was unexpected. If the SAE is assessed to be both drug-related and unexpected, the Sponsor or designee will notify all Investigators, and will report it to the appropriate regulatory authorities as required by applicable local regulations. The Sponsor or designee will report SAEs, including narratives, to the U.S. FDA and local regulatory authorities as required by 21 CFR 312.32 and the International Conference on Harmonisation (ICH) Guideline for Good Clinical Practice. The Investigator is responsible for notifying his/her respective IRB.

9.6. Other Reportable Events

All pregnancies occurring during the study must be followed for information regarding the course of pregnancy, delivery, and condition of the newborn. Follow-up should be provided by the Investigator to the Sponsor-designated Medical Monitor in a timely manner. When the newborn is healthy, further follow-up is not necessary. Male subjects must inform the Investigator if their partner becomes pregnant during the study.

10. SCHEDULE OF PROCEDURES

The schedule of procedures is summarized in [Table 3](#).

10.1. Visit 1 and Screening Period (Week -4 to Week -1)

The subject will be asked to provide written, informed consent for this study before any required procedures are performed. This study may employ electronic informed consent. Electronic or digital signatures (compliant with 21 CFR § 11 regulations for collecting and storing digital signatures) may be captured indicating the patient’s willingness to participate in the clinical trial. The use of electronic informed consent supplements the interaction between the participant and the research staff, and it provides an opportunity for remote conduct of study activities in the setting of the COVID-19 Health Emergency. Subjects will also be asked by site staff to sign an additional consent for their inclusion in a secure, proprietary research subject database maintained by Verified Clinical Trials (VCT) [Verified Clinical Trials, Garden City, NY]. The database will use partially identified subject information to review subjects’ research study history within the database. Subjects who meet any of the following criteria will not be eligible for continued

screening: current enrollment in another study, concurrent screening at another research site, violation of the required number of half-lives of the investigational product of the prior research study, violation of the washout period between studies, incorrect age for the NYX-2925-2005 study, or previous randomization into a clinical trial of NYX-2925. Employees, contractors, or volunteers of the study site, Contract Research Organization (CRO), or Aptinyx, or relatives of any employee, contractor, or volunteer of the study site, CRO, or Aptinyx are not eligible to participate. Serious adverse event collection begins after the informed consent is obtained and adverse event collection begins after study drug administration.

There may be up to three components in the screening period for this study: 1) After providing informed consent, subjects will participate in a screening visit where medical history, concomitant medications, scales, and eligibility to participate will be assessed; 2) Subjects who meet eligibility requirements and are taking an analgesic medication for pain related to fibromyalgia will then be required to discontinue the analgesia from one to four weeks (see [Section 15.1](#) of the protocol for Disallowed Analgesic and Other Medications). Subjects taking no concomitant analgesic medication for their fibromyalgia at Visit 1 may directly begin Week - 1 of the Screening Period; 3) During this time, subjects will be provided a handheld device to record their pain and rescue medication use.

After the informed consents are signed, the following procedures and assessments should be completed at Visit 1:

- Demographic characteristics (age, sex, race, and ethnicity)
- Medical history
- Prior (within last 30 days) and concomitant medications
- PGI-S
- S-STS
- [REDACTED]
- MINI
- Adverse events
- Confirmation that subjects meet the 2016 American College of Rheumatology criteria for fibromyalgia
- Height and body weight
- Vital signs (blood pressure and pulse after sitting or lying supine for at least five minutes)
- Complete physical examination, including comprehensive neurological examination
- Triplicate electrocardiograms after five (5) minutes in supine position with a minimum of a two minute interval between ECGs
- Blood samples for fasting (8 hours) serum chemistry and hematology
- Blood samples for Human immunodeficiency virus (HIV) and hepatitis screening
- Urine sample for urinalysis

- Urine pregnancy test for females of childbearing potential
- Urine drug test

Eligible subjects who meet all inclusion and exclusion criteria will enter the 1- to 4-week Screening Period. The following procedures and assessments will be performed:

- Subjects will discontinue all analgesic treatments for pain related to fibromyalgia, and complete daily pain diaries. The duration of their Screening Period will depend upon the analgesic treatment that is being discontinued, but the total duration of the Screening Period cannot exceed four (4) weeks (see Section 15.1 of the protocol for Disallowed Analgesic and Other Medications). Subjects taking no concomitant analgesic medication may directly begin Week -1 of the Screening Period.
- Subjects will be provided a handheld device for pain reporting and, as a method for ensuring consistency and reliability of pain scoring, subjects will be instructed at all study visits how to record their pain score on the device and rescue medication use. Subjects will be educated at screening and reminded at other visits on appropriate expectations for their participation in a clinical study and the importance of consistently and accurately reporting their pain throughout the study. On each day preceding the Baseline Visit: (Week 0/Visit 2), subjects will record the following on the handheld device:
 - At bedtime: average pain intensity and use of rescue medication during the past 24 hours
 - Upon waking: DSIS
- Subjects will be dispensed acetaminophen to be used as rescue medication and will be instructed to take no more than 3 g/day (one to two 500 mg tablets every 6 hours as needed) for pain related to fibromyalgia.

10.2. Baseline Visit: Week 0/Visit 2

At Week 0 (Visit 2), the following procedures and assessments will be performed/assessed:

- Concomitant medication use
- PGI-S
- S-STS
- Adverse events
- Vital signs (blood pressure and pulse after sitting or lying supine for at least five minutes)
- Electrocardiogram after five minutes in supine position
- Blood samples for fasting (8 hours) serum chemistry and hematology
- Urine sample for urinalysis
- Urine pregnancy test for females of childbearing potential
- Urine drug test

- Rescue medication return, assessment of appropriate use by inventory of returned tablets, as well as by subject interview
- Verify eligibility with inclusion and exclusion criteria

Pain scores reported by subjects during the Screening Period will be evaluated by the IRT system for raw score and for variability among scores after automated transmission of pain scores from the handheld devices to determine randomization eligibility. The IRT system will notify the site if the subject is “Eligible” or “Not eligible.” No other information will be provided.

Subjects who continue to meet all entry criteria and are randomized by the interactive response technology system will undergo the following procedures and assessments:

- FIQR
- PROMIS_{FM} (sleep disturbance, fatigue profile, and physical function)
- [REDACTED]
- Dispensing of study drug – Subjects will take their first dose in the clinic. They will be instructed to take the study drug daily and confirm they have taken study drug in the handheld device each day.
- Re-dispensing/dispensing of rescue medication – Subjects will be reminded not to exceed 3 g/day (one to two 500 mg tablets every 6 hours as needed) for pain related to fibromyalgia
- Subjects will be reminded on how to record their pain score on the device and will also be reminded about appropriate expectations for their participation in a clinical study and the importance of consistently and accurately reporting their pain intensity throughout the study. Refresher training of these educational materials will be repeated at each site-based study visit via the aLearn® portal, with the exception of the final visit. On each day until returning to the study site, subjects will record the following on the handheld device:
 - At bedtime: average pain intensity and use of rescue medication during the past 24 hours.
 - Upon waking: DSIS and confirm when study drug has been taken
- The subject will be given a printed copy of the study specific S-STS to take home and complete during the Week 2 (Visit 3) telephone or videoconference visit.

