Eligible subjects who meet all entry criteria will enter a 1- to 4-week Screening Period, during which they will discontinue all their analgesic treatments for pain related to fibromyalgia, and complete daily pain diaries. The duration of the Screening Period will depend upon the analgesic treatment that is being discontinued (see Section 15.1 of the protocol for Disallowed Analgesic and Other Medications). The discontinuation of analgesic medication(s) will be managed by the Principal Investigator or designee at

the investigative site, as applicable. Subjects taking no analgesic medication at Visit 1 may directly begin Week -1 of the Screening Period.

During Visit 1, eligible subjects will be provided a handheld device and, as a method for ensuring consistency and reliability of pain scoring, subjects will be instructed at all study visits on how to record their pain scores and rescue medication use on the device. Subjects will also be educated at screening on Accurate Pain Reporting® and Placebo Response Reduction® (APR® and PRR® training [Analgesic Solutions, Wayland, MA]) and provided refresher training at all site-based study visits, via the aLearn® learning management system portal (Analgesic Solutions, Wayland, MA). This training is mandatory prior to randomization and at each site-based visit throughout the study, with the exception of the final visit. Subjects will be reminded at all visits of appropriate expectations for their participation in a clinical study and the importance of consistently and accurately reporting their pain throughout the study.

Subjects will be dispensed acetaminophen to be used as rescue medication (RM) and will be instructed to take one to two 500 mg tablets every 6 hours as needed for pain related to fibromyalgia, not to exceed three (3) grams of acetaminophen per day.

For pain unrelated to fibromyalgia, subjects may use a nonsteroidal anti-inflammatory drug (NSAID) for up to two (2) days during a seven (7) day period. If the need for analgesics exceeds this period, the patient should call the Investigator to evaluate the cause of pain and the course of action. If a subject requires a NSAID for pain unrelated to fibromyalgia, the medication should be recorded as a concomitant medication and the adverse event must be recorded in the eCRF.

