pain scores from the handheld devices to determine randomization eligibility. Subjects whose mean of the daily average pain intensity score during the preceding seven (7) days is within the protocol-defined algorithm and whose compliance with daily diary completion is found to be adequate will be eligible for randomization. The absolute pain scores and variability among scores, as well as the actual percentage required for diary compliance, will be masked to investigators and subjects. Subject eligibility for randomization into the study based on these variables will be communicated to the investigator via the IRT system. The IRT system will notify the site if the subject is "Eligible" or "Not eligible." No other information will be provided.

Eligible subjects will be randomized to receive either oral NYX-2925 50 mg, NYX-2925 100 mg or placebo daily for 12 weeks. Investigators and subjects will be both blinded to treatment allocation and masked to the randomization criteria.

Subjects will be dispensed a four-week supply of study drug and instructed to take one (1) capsule by mouth once daily. The first dose of study drug will be taken in the clinic during Visit 2 (Week 0). Subjects will be instructed to take study medication one time per day throughout the study. Acetaminophen will be dispensed/re-dispensed for use as rescue medication for pain related to fibromyalgia; instructions to take no more than 3 g/day (one to two 500 mg tablets every 6 hours as needed) will be reinforced.

Adverse event collection will begin from the time of study drug administration through the last day of the subject's participation in the study.

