Study Period	Screening		Baseline		Treatment Period		
	Study Week	1 to 4 weeks ^a (-28 to -1)	Week 0 ^d (1 ±2)	Week 2 (14 ±2)	Week 4 (28 ±4)	Week 8 (56 ±4)	Week 12 ^b (84 ±4)
Study Visit	Visit 1	Visit 2	Visit 3 ^v	Visit 4	Visit 5	Visit 6	
Record average pain intensity ^m and rescue medication use over past 24 hours at bedtime for each day	X	X	X	X	X	X	X
Randomize eligible subjects		X					
Dispense study drug ^o		X					
Confirm subject takes first dose of study drug (in the clinic)		X					
Confirm study drug dosing each day via handheld device		X	X	X	X	X	X
Return study drug and assess compliance ^l			X	X	X	X	X
Misuse, Abuse, and Diversion Drug Event Reporting System [®] (MADDERS) ^s				X	X	X	X
Record Daily Sleep Interference Scale (DSIS) each morning ⁿ	X	X	X	X	X	X	X
Assess handheld diary compliance		X	X	X	X	X	X
MINI International Neuropsychiatric Interview (MINI)	X		X	X	X	X	X
Fibromyalgia Impact Questionnaire – Revised (FIQR)				X	X	X	X
Patient Reported Outcomes Measurement Information System – Fibromyalgia (PROMIS _{TM}) ^t			X	X	X	X	X
Patient Global Impression of Change (PGI-C) scale					X	X	X
Sheehan Suicidality Tracking Scale (S-STS)	X	X	X ^v	X	X	X	X
Concomitant medications ^q	X	X	X	X	X	X	X
Adverse events ^r	X	X	X	X	X	X	X
Safety follow-up calls							X ^y

^a Subjects will discontinue all concomitant analgesic medications taken for pain related to fibromyalgia. Duration of the period will depend upon the analgesic(s) being discontinued, not to exceed 4 weeks. Subjects not taking any concomitant analgesic medications at Visit 1 may directly begin Week -1 of the Screening Period.

^b ET=Early Termination. Subjects who prematurely discontinue randomized treatment will have Week 12 procedures performed. Diary completion ends the night before the Week 12 visit.

^c Informed consent includes an additional consent for inclusion in a secure, proprietary, research subject database to screen for protocol violators. The main informed consent document may be executed up to 30 days prior to the screening visit. The date the first screening related activity is completed will be considered the subject's screening date. If the subject does not complete the screening visit within 30 days of signing the informed consent document, the subject must be reconsented.

^d Verify subject still meets all inclusion criteria and does not meet any exclusion criteria.

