12.7.1. Adverse Events

A TEAE is defined as an adverse event with an onset that occurs after receiving study drug, or a continuing adverse event diagnosed prior to the date of first dose of study drug that increases in severity after the start of dosing. Adverse events will be categorized by system organ class and preferred term with the Medical Dictionary for Regulatory Activities (MedDRA).

Summary tables for TEAEs will include number and percent of subjects experiencing TEAEs by system organ class and preferred term. If a subject has more than one TEAE that codes to the same preferred term, the subject will be counted only once for that preferred term. Similarly, if a subject has more than one TEAE within a system organ class category, the subject will be counted only once in that system organ class category.

The following TEAE summaries will be provided for the Treatment Period:

- Overall summary of TEAEs
- TEAEs by system organ class and preferred term
- Drug-related TEAEs by system organ class and preferred term
- TEAEs by system organ class, preferred term, and severity
- Serious TEAEs by system organ class and preferred term
- TEAEs leading to study drug discontinuation by system organ class and preferred term

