15. APPENDICES

15.1. Disallowed Analgesic and Other Medications*

Washout of the following disallowed analgesics should be completed during screening, with the last dose being at least 2 weeks prior to randomization.

- Tricyclic antidepressants (TCAs)
- Norepinephrine reuptake inhibitors (NRIs), e.g., atomoxetine (Strattera[®]) and bupropion (Wellbutrin[®], Zyban[®])
- Serotonin-norepinephrine reuptake inhibitors (SNRIs), e.g., milnacipran (Savella), duloxetine (Cymbalta[®]), venlafaxine (Effexor[®]), Desvenlafaxine (Pristiq[®]), levomilnacipran (Fetzima[®])
- Anti-epileptics, e.g., gabapentin (Neurontin[®]) and pregabalin (Lyrica[®]); NMDA receptor ligands
- Opioids
- NSAIDs (except as described in section 8.7)
- Benzodiazepines except alprazolam or lorazepam
- Muscle relaxants
- Acetaminophen or acetaminophen containing therapies for indications other than fibromyalgia
- Topical therapies: topical capsaicin; topical/local anesthetic lidocaine

*Any non-pharmacologic therapies or interventions for treatment of pain that are not on this list needs to be discussed with the Medical Monitor prior to screening (e.g., nerve blocks, spinal stimulators, etc.).

Subjects must be stable for at least seven (7) days prior to randomization. The “stable” condition is based on investigators’ clinical judgment. It means no significant withdrawal effects, and to be stable regarding their pain, i.e., subjects should not be in a flare state with much worse pain than before washout as is common with discontinuation of any drugs but most common with NSAIDs and opioids.

Prohibited medications must not be withdrawn for participation in this study when prescribed for a condition other than pain.

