6.12.1 Adverse Events

Adverse events will be collected from the time of study drug administration through the last day of the subject's participation in the study.

A treatment emergent adverse event (TEAE) is defined as:

- Any AE that has an onset on or after the first dose of study drug, through the last day of the subject's participation in the study
- Any pre-existing AE that has worsened in severity on or after the first dose of study drug, through the last day of the subject's participation in the study

A treatment-related AE is defined as an AE classified by the Investigator as 'Related' to the study drug. If an AE has missing relationship it is assumed to be related to the study drug for analysis purposes.

Maximum severity (Life threatening) will be assumed for an AE with missing severity.

An overall summary table of AE incidence (number and percent of subjects) and number of events, will be presented by treatment group and overall, for the following categories:

- Any TEAE
- Treatment-Related TEAEs
- Serious TEAEs

- Serious Treatment-Related TEAEs
- TEAEs Leading to Study Drug Discontinuation
- TEAEs Leading to Early Withdrawal
- TEAEs Leading to Death

Summaries of TEAE incidence and number of events by SOC and PT will be presented by treatment group and overall, for the following:

- TEAEs
- Treatment-related TEAEs
- Serious TEAEs
- Serious Treatment-Related TEAEs
- TEAEs Leading to Study Drug Discontinuation
- TEAEs by Maximum Severity, (incidence only)
- Treatment-Related TEAEs by Maximum Severity, (incidence only)

The following listings of AEs will be presented in Section 14.3.2 of the CSR:

- Serious AEs
- AEs Leading to Early Withdrawal
- AEs Leading to Death

AE tabulations will be presented by SOC and PT in descending overall frequency of AE incidence and then alphabetically for ties.

All reported AEs will be listed in Appendix 16.2.7 of the CSR.

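### Non-serious adverse events are collected only from first dose, so those starting after Visit 1 have no scheduled record of onset and severity, although the visit lists and TEAE definitions refer to pre-dose adverse events

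*Protocol*

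**What the plan says.** The start of collection is stated in the same way throughout. The synopsis (Baseline Visit) says "Adverse event collection will begin from the time of study drug administration through the last day". Footnote r of Table 3, protocol 9.4.2 and 9.4.3 and SAP 6.12.1 agree, and Section 10.1 adds the split by seriousness: "Serious adverse event collection begins after the informed consent is obtained and adverse event collection begins after study drug administration".

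The visit lists read differently. Section 10.1 includes "Adverse events" among the Visit 1 procedures. Section 10.2 has the same unqualified item in its opening list, ahead of the eligibility check, randomization and first dose. The Table 3 row "Adverse events ^r" is marked at screening and baseline as well as on treatment.

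The TEAE definitions look back before dosing. Protocol 12.7.1 counts "a continuing adverse event diagnosed prior to the date of first dose of study drug that increases in severity after the start of dosing". SAP 6.12.1 counts "Any pre-existing AE that has worsened in severity on or after the first dose of study drug".

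Section 9.4.2 treats whatever is present before dosing as a pre-existing condition belonging to medical history. Its worsening in frequency, intensity or character becomes reportable as an adverse event. Table 3 and Section 10.1 place medical history at Visit 1 only.

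Section 15.1 requires disallowed analgesics to be washed out in screening, with at least two weeks between last dose and randomization. It also requires seven days of stability before randomization, and says that "subjects should not be in a flare state with much worse pain than before washout as is common with discontinuation of any drugs".

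**The concern.** Safety and tolerability is one of the two primary objectives (protocol 5.1). The interval between Visit 1 and first dose is one in which the protocol itself has some subjects stop opioids, SNRIs, tricyclics, anti-epileptics, muscle relaxants or NSAIDs, and in which it foresees withdrawal effects and flares.

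If the collection rule is followed as written, non-serious events in that interval are not collected as adverse events. A symptom that begins in washout and carries on after Day 1 then depends on site practice. A site working from the visit lists may record it before dosing. A site working from the collection rule may enter it after Day 1 as a new event, or leave it out. Section 4 of the protocol names headache among the most commonly reported TEAEs for this drug, so whether a given headache predates Day 1 is a practical question. The worsened part of the TEAE definition needs a prior severity to compare with, and for these events none is scheduled to be recorded. Events following a withdrawal that the study requires are also not tabulated.

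**Working it through.** The plan gives no figure on this point, so the check sets the rules side by side and follows each kind of pre-dose event through them.

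1. **Serious event at any time after consent.** Collected from consent (Table 3 footnote r, Sections 9.5 and 10.1). No gap.
2. **Non-serious condition already present at Visit 1.** Goes to medical history, and its worsening after dosing is reportable (Section 9.4.2). Onset can be documented. Section 9.1.1 specifies no severity grade for medical history; the severity scale in 9.4.3.1 is for adverse events.
3. **Non-serious event that starts after Visit 1 and is still present at first dose.** It meets the 9.4.2 definition of pre-existing, because that definition turns on dosing and not on screening. But the only scheduled medical history has already been taken, Section 10.2 does not update it, and SAP 6.7 tabulates conditions by their status at screening. Onset and severity have no scheduled record.
4. **Non-serious event that starts and resolves between Visit 1 and first dose.** It falls outside the adverse event window and comes after the medical history visit. No explicit place is given.

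Cases 3 and 4 are the gap. For case 3, the worsened part of both TEAE definitions refers to a pre-dose adverse event that the collection rule does not create.

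The date rules in SAP 6.2.5 add to case 3. An ongoing event with no start date is assigned the date of first dose. So is an ongoing event with only month and year known, when that month is the month of first dose. A washout symptom entered later with an incomplete onset date can thus become treatment-emergent by imputation.

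Length of the window, counted from Visit 1:

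- Subjects who wash out at or after Visit 1: at least 2 weeks × 7 = 14 days from last disallowed dose to randomization (Section 15.1), within a Screening Period of at most 4 weeks × 7 = 28 days (Section 6.1).
- Subjects on no analgesic: they may enter Week -1 directly, so about 7 days.
- Treatment Period: 12 × 7 = 84 days.
- Ratios to treatment time: 14/84 = 17%, 28/84 = 33%, 7/84 = 8%.

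The documents give neither the share of subjects who wash out nor a rate of symptoms in washout, so no count of affected subjects can be derived.

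**The case against.** The strongest reply is that the documents already contain a coherent system. The start rule never varies. Footnote r attaches it to the Table 3 row, so the Visit 1 mark can mean serious events only, and the synopsis lists only serious event collection at Visit 1. Visit 2 includes the first dose in clinic, so adverse events can arise that day. Pre-dose conditions have a home in medical history, and SAP 6.2.5 applies its date rules to medical history too. Worsening is reportable under 9.4.2, and 9.4.3.1 has changes in severity recorded separately with their own onset dates. A worsening after Day 1 could therefore qualify as a new-onset TEAE.

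Much of this stands. Table 3 is largely reconciled by its footnote; the firmer mismatch is in the Section 10.1 and 10.2 lists, which carry no such limit. The seven-day stability condition restricts the continuing withdrawal symptom that matters most. Washout applies only to subjects on disallowed medication, needs the investigator to find it medically appropriate, and excludes drugs prescribed for conditions other than pain. Pain and sleep interference are also in the diary before baseline. The instruction that with NSAID use "the medication should be recorded as a concomitant medication and the adverse event must be recorded in the eCRF" appears in the screening text but is repeated in Section 8.7 as a study-wide rule, so it is at most a local mismatch.

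What the reply does not supply is a scheduled occasion, after Visit 1 and before dosing, to record onset and severity of a non-serious event. Reporting a worsening under 9.4.2 still requires knowing what it worsened from.

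**Conclusion.** The concern holds in a limited form. The collection start, the visit lists in 10.1 and 10.2, the Visit 1-only medical history and the two TEAE definitions do not fit together for non-serious events that begin after Visit 1. Those events have no scheduled record of onset and severity, and the ones that resolve before dosing have no explicit place.

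A reader might go further and infer that all pre-dose events are lost, that no form exists for them, or that the worsened part of the TEAE definition is empty. The documents do not support this. Serious events are collected from consent, conditions present at Visit 1 enter medical history, and the eCRF is not among the documents. Nor do they support a number of affected subjects per arm.

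The effect is on the classification and completeness of the safety tables, which are descriptive (protocol 12.7). Background symptoms from washout would be expected in all randomized arms, so they would blur a comparison more than favour one arm. The efficacy analyses are unaffected. The conclusion assumes that sites follow the schedule as written and that medical history is not updated at Visit 2 by an instruction outside these documents.

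**What to change.** Record non-serious events from consent, with onset date and severity, at the Visit 1 and Visit 2 entries that Sections 10.1 and 10.2 already list. Flag those with onset before first dose as pre-treatment, tabulate them separately, and use their recorded severity as the reference for the worsened part of the TEAE definition. Bring the synopsis, Table 3 footnote r, protocol 9.4.2, 9.4.3, 10.1 and 12.7.1, and SAP 6.12.1 into line.

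Updating medical history at Visit 2 with onset and severity would be an alternative for events still present at dosing. To cover events that have resolved by then, the update would have to ask for them explicitly.

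The cost is wording, a few more adverse event records and queries, and one extra table.
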